**Version Date: 5/1/2018** 

16.3. **Describe how missing data will be handled.** Missing data will be excluded from analysis.

- 16.4. Describe plans for interim analysis and early stopping rules (if applicable). N/A
- 16.5. Describe under what circumstances will un-blinding occur and the procedures to do so (if applicable). N/A

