**Version Date: 5/1/2018** 

Name of Questionnaire/Instrument	How will the questionnaire/instrument be administered? (Examples: study personnel, self-administered, computer, etc.)	Who answers the questionnaire? (Examples: parent, child)	If modified after initial approval, note current revision date:
Parent SPARCK intervention survey (Appendix A)	Self-administered on iPad®	Parent	
Parent SPARCK Placebo Survey (Appendix B)	Self-administered on iPad®	Parent	
Parent post-visit satisfaction survey (Appendix E)	Self-administered on paper	Parent	
Parent Eligibility Survey (Appendix F)	Study personnel verbally	Parent	
Parent demographic survey (Appendix G)	Self-administered on paper	Parent	
Provider Baseline Survey (Appendix K)	Self-administered electronically	Provider	
Provider Follow-Up Survey (Appendix L)	Self-administered electronically	Provider	
Vaccine data collection form for Allegro Pediatrics sites	Study personnel	Study personnel	

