**Version Date: 5/1/2018** 

#### **Investigator Help**

## 11. Investigational Plan

## 11.1. Describe the general schema of the study design.

Figure 1. Study Design

This study is a cluster randomized controlled trial. We will pair up to 30 Seattle area primary care clinics and Group Health primary care clinics based upon the number of vaccine doses ordered and enroll and randomize clinics to control and SPARCK arms. We will screen parents for vaccine hesitancy using the Parent Attitudes about Childhood Vaccines Short Form survey (PACV-SF) (Appendix F). Parents in the SPARCK arm of the study will take the intervention survey (which has the PACV embedded in it) to their child's 2 and 6 month visits (Appendix A) whereas parents in the control arm of the study will take a placebo survey about childhood health topics (Appendix B). The results of these surveys will be communicated to the child's provider (Appendices C and D). After the child's 6 month visit, parents in both arms will complete a satisfaction survey about their visit experience (Appendix E). When the child is 8 months of age, we will use an automated clinic immunization database to determine their immunization status. For participants who were lost to follow up (i.e. those who did not have a 6 month appointment, or those who did not have a 2 and 6 month appointment), we will also use Washington State Immunization information System records to determine participant immunization status.

Study Title: Screening Parents about Recommended

Care for Kids (SPARCK) Study

Principal Investigator: [name], MPH

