#### 13. Study Procedures

This section should list the procedures, observations, measures, etc. at each study visit, including history, examination, study drug administration or other interventions (can be provided in table form as a Table of Evaluations often used in protocols).

13.1. **Describe study visits.** Parents will be approached and screened for this study by a research assistant (RA) over the telephone (Group Health parents only) or at their child's clinic upon check-in for their child's health supervision visit that occurs at or before 2 months of age. For Group Health parents who are screened over the telephone, an RA will meet the parent at their child's 2 month health supervision visit to complete the consent and enrollment process. This enrollment encounter will include having the parents who are eligible and agree to participate complete the demographic survey (Appendix G). If enrollment occurs at a health supervision visit prior to 2 months of age, an RA will meet the parent back at their child's clinic at the time of their child's 2 month health supervision visits to have them complete an electronic version of the study survey using an iPad® (i.e. the intervention survey at SPARCK clinics (Appendix A) and the placebo survey at control clinics (Appendix B)). If enrollment occurs at the 2 month health supervision visit, the RA

Study Title: Screening Parents about Recommended

Care for Kids (SPARCK) Study

Principal Investigator: [name], MPH

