#### **Analysis Plan and Statistical Methods**

16.1. Outline the data analysis plans relating to each specific aim/objective or research hypothesis mentioned in section 11 above. It should be clear how the analysis results will allow each aim/objective to be answered. The analysis plans for the primary aim should be detailed. Analysis plans for secondary aims may be brief, but must be included. Give the names of specific statistical methods and state which variables will be used with them.

Aim1: To evaluate the effectiveness of the SPARCK intervention in increasing vaccine acceptance. We will conduct an intention-to-treat analysis for Aim 1. Parents will be the unit of analysis. We will examine baseline characteristics among control and SPARCK parents using Pearson's  $\chi 2$  tests (or Fisher's exact tests) for categorical variables and t-tests for continuous variables to assess for any unbalanced confounders between control and SPARCK arms. To compare our primary outcome of percent days underimmunized between control and SPARCK arms, we will apply linear mixed effects regression modeling to the percent days under-immunized with clinic-specific random-effects to account for within-clinic correlation. If unbalanced confounders are detected between arms, they will be adjusted for in the mixed effects models.

Aim 2: To assess how parent-rated experience of the vaccine discussion changes as a function of the SPARCK intervention. For Aim 2, we will use Pearson's χ2 test to compare parent (binary) ratings of their vaccine discussion between control and SPARCK

Study Title: Screening Parents about Recommended

Care for Kids (SPARCK) Study

Principal Investigator: [name], MPH

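### If covariate adjustment is triggered, the blanket exclusion rule in 16.3 would drop parents with a known outcome from the Aim 1 and Aim 2 models because an adjusted baseline item is blank

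*Combined protocol and SAP*

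**What the plan says.** Section 16.3 is the whole missing-data plan: "Missing data will be excluded from analysis". It names no aim and draws no line between outcomes and covariates.

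Section 16.1 states for Aim 1: "We will conduct an intention-to-treat analysis for Aim 1". The model is given as: "we will apply linear mixed effects regression modeling to the percent days under-immunized with clinic-specific random-effects". Baseline characteristics are compared between arms by significance tests, and then: "If unbalanced confounders are detected between arms, they will be adjusted for in the mixed effects models". For Aim 2, section 16.1 likewise uses a mixed logistic model that accounts for unbalanced parent factors.

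The outcome and the covariates come from different sources. For the primary outcome, section 11.1 says that at 8 months of age "we will use an automated clinic immunization database to determine their immunization status"; for families lost to follow-up, "we will also use Washington State Immunization information System records to determine participant immunization status". The demographic items come from a survey (Appendix G) that section 5.2 lists as self-administered on paper and that section 13.1 places in the enrolment encounter.

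Section 11.10 treats withdrawal as missing data and says that the sample size allows for the expected attrition. No section provides imputation, a missing category or a sensitivity analysis.

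**The concern.** A regression model with a covariate cannot use a record in which that covariate is blank, unless the plan says how to fill it. Read together, 16.1 and 16.3 therefore remove a parent from the adjusted model when an adjusted baseline item is blank, even when the child's immunization record is complete. The plan goes to the state registry to recover outcomes for families lost to follow-up. It would then discard outcomes already in hand for want of a demographic answer.

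Precision is at stake, and so is the completeness of the analysis set in an analysis described as intention-to-treat. The point concerns only parents whose outcome is known. Withdrawn families and missing outcomes are a different question.

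**Working it through.** **When a parent is lost.** Three things must coincide:
1. the baseline comparison flags an imbalance (16.1);
2. the flagged item enters the model;
3. the parent's value for that same item is blank.

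The model with arm and clinic random effects alone loses nobody to blank survey items.

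**Inputs from section 16.2.** 160 parents, 80 per arm, 16 clinics of 10; SD 33.3 points; intraclass correlation 0.02; alpha 0.05 (taken as two-sided, since the section does not say); stated power 90%; target decrease of 30 days per vaccine from birth to 8 months.

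**Assumed, because the documents give no figure.** The number of adjusted items k, the blank rate per item p, and independence of blanks between items.

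**The plan's own figure.** Taking birth to 8 months as 243 days, 30/243 = 12.35 points. The design effect is 1 + 9 × 0.02 = 1.18. For 90% power this needs 181 per arm, and 80 per arm gives about 58%. The stated 160 is thus not reproduced at this effect. That is a separate matter on which the present point does not depend. To show the loss relative to the stated 90%, I use the difference at which 80 per arm does give 90%:

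- SE = 33.3 × sqrt(2 × 1.18 / 80) = 5.72 points
- difference = (1.960 + 1.282) × 5.72 = 18.5 points

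**Formulas.**
- Share kept: f = (1 − p)^k
- Parents per arm: 80f; average clinic size: 10f; design effect: 1 + (10f − 1) × 0.02
- Power = Phi(difference / SE − 1.96), with SE recomputed for each f

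**Results.**

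| Adjusted items | Blank rate | Parents kept | Lost | Power at 18.5 points | Power at 12.35 points |
|---|---|---|---|---|---|
| none | – | 160 | 0 | 90.0% | 57.9% |
| 1 | 2% | 157 | 3 | 89.5% | 57.2% |
| 1 | 5% | 152 | 8 | 88.7% | 56.1% |
| 3 | 2% | 151 | 9 | 88.5% | 55.8% |
| 3 | 5% | 137 | 23 | 86.0% | 52.5% |

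Worked line for three items at 5%: f = 0.95^3 = 0.857; 80f = 68.6; design effect = 1 + 7.57 × 0.02 = 1.151; SE = 33.3 × sqrt(2 × 1.151 / 68.6) = 6.10; 18.54 / 6.10 − 1.96 = 1.08; power 86.0%.

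If the blanks fall on the same parents, the loss shrinks towards the one-item line: about 8 parents at 5% rather than 23.

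**The case against.** The strongest reply is that 16.3 can be read narrowly. The only other use of the term, in 11.10, refers to withdrawal, so the plan may be silent on covariates rather than ordering deletion. That is fair as a reading, but it does not help: with no filling rule, the model omits the record anyway.

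Second, adjustment is conditional. This stands in full. A reader might infer that the primary model will lose parents; the documents support only that it would do so if an imbalance brings in an item with blanks.

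Third, a reader might infer that blanks are frequent because the survey is on paper. The documents do not show this. The form is completed at an enrolment encounter attended by a research assistant, who could check it. Appendix G is not available here. Not every baseline characteristic comes from that form either: the eligibility items are asked verbally and are needed for entry.

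Fourth, a reader might conclude that intention-to-treat is abandoned. That goes too far. Parents would still be analysed in the arm of their clinic; the defect is an incomplete analysis set.

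The 10% attrition allowance in 16.2 does not answer the point, since it concerns loss over the course of the study and not blank baseline items. The power figures also ignore any precision gained from adjustment.

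**Conclusion.** The point holds in conditional form. As written, 16.3 and 16.1 together would drop parents with a known outcome from the Aim 1 or Aim 2 model if a covariate with blank values is adjusted for, and nothing elsewhere in the plan prevents it. The loss runs from negligible (about 3 of 160, power about 89.5%) to moderate (about 23 of 160, power about 86%). These figures rest on assumed blank rates, an assumed number of adjusted items, independence between items, and an 18.5-point difference chosen to match the stated 90% power. The documents cannot narrow the range.

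Two stronger readings should not be drawn. First, filling blanks is not guaranteed to leave the arm effect free of bias. Clinics are randomised and parents enrol individually at them, so blanks may differ by arm. Second, the way baseline tests choose the covariates, and so the families analysed, is a separate weakness. The change below removes its effect on who is analysed but leaves the data-driven choice of covariates in place.

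The change is worth making because it is cheap and keeps outcomes that the trial has already collected.

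**What to change.** Amend 16.3 to say that:
- exclusion applies only to a missing outcome;
- a blank baseline covariate does not remove a parent from the Aim 1 or Aim 2 models;
- blank covariates are filled without using arm or outcome, for example with the mean over both arms for continuous items and a 'missing' category for categorical items;
- a complete-case fit may be reported as a sensitivity analysis, with the number of parents in each model.

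Other filling methods would serve if fixed in advance. The wording should also be reconciled with the intention-to-treat statement in 16.1.

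The cost is one or two sentences and trivial programming. The downside is slightly incomplete adjustment for parents with filled values. It matters somewhat more here than in an individually randomised trial, because clinics are randomised and the covariates are adjusted precisely because they appear unbalanced. Having the research assistant check the form for blanks at enrolment would reduce the problem at source.

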## 17. Safety and Adverse Event Management

**Note:** You may refer to the Data Safety Monitoring section in the application for your answers in this section if this is an initial LIP. If any of these plans is modified at some point in time after initial study approval, then the modifications should be described in this section as part of a subsequent LIP.

## Safety and Adverse Event Monitoring

- 17.1. Describe methods used to ensure participant safety monitoring. Include specific management plans for expected or unexpected adverse events as applicable.

  See Data Safety Monitoring section of application.
- 17.2. If there are specific criteria for study drug/intervention, modification or discontinuation for adverse reactions, they should be described here. N/A

#### **Monitoring Plan**

17.3. Describe Monitoring Plan.

See Data Safety Monitoring section of application.

#### **Adverse Event Reporting**

17.4. Describe how adverse events will be defined, graded, and reported. If there are any potential adverse events that will not be considered related to the study, these should be described here.

See Data Safety Monitoring section of application.

## **Investigator Help**

#### **Data Collection Procedures for Adverse Events**

17.5. Indicate who will be collecting and reviewing adverse events and with what frequency.

See Data Safety Monitoring section of application.

## **Review of Study Conduct and Safety Data**

Study Title: Screening Parents about Recommended

Care for Kids (SPARCK) Study

Principal Investigator: [name], MPH

**Version Date: 5/1/2018** 

17.6. Describe who (individual or group) will periodically review the study conduct and data to assess safety for current or future participants. Include what data will be reviewed and the frequency of the review.

Drs. [name] (PI), [name] (co-investigator) and [name] (co-investigator) will monitor the progress of the trial through quarterly assessments of data quality and timeliness, participant recruitment, accrual and retention, participant risk versus benefit, and other factors that could affect study outcomes. We will make quarterly determinations regarding continuation or conclusion of the trial based on these assessments.

#### **Investigator Help**

#### 18. Data/Specimen Sharing

18.1. Discuss if data or samples will be shared with other investigators outside of the research team. Provide details as to when the data/samples will be shared (eg during trial, banked for future indefinite use), who will have access to the data/samples, how access will be controlled and whether data/samples will be coded or de-identified. Data will not be shared outside the research team.

- 19.2. Research Team's Previous Experience in Conducting This Type of Study. Describe the previous experience of the Principal Investigator and/or study team in conducting this type of study. This can include unpublished and in-progress endeavors as well as published reports. Participation in studies which used a similar research design, but in a different setting/patient population may also be considered relevant. If the investigators have not participated in any preliminary studies leading up to the current one, please reply "None" to this question.
  - [name] has extensive experience using survey methods and qualitative analyses similar to that proposed in this project. This projects builds upon earlier Seattle Children's Research Institute-funded work that he conducted as PI to develop the Parent Attitudes about Childhood Vaccines (PACV) survey and evaluate its construct validity, predictive validity, and test-retest reliability. These foundational projects yielded 3 peer-reviewed publications and helped foster a strong collaborative relationship with investigators at Group Health Research Institute/Group Health Cooperative. To develop his overall research program, he successfully competed for NIH support through the K23 mechanism and has efficiently and effectively administered his K23-associated projects: he has

Study Title: Screening Parents about Recommended

Care for Kids (SPARCK) Study

Principal Investigator: [name], MPH

**Version Date: 5/1/2018** 

provided leadership and oversight to research staff, fostered research collaborations, and to date has published two manuscripts. This, in combination with his clinical and research training in general pediatrics and health services research, has provided him with the research environment, expertise and insight needed to successfully conduct and complete the proposed work. In summary, he is an early stage investigator with a productive research record and the relevant background and research skills needed to successfully lead and conduct the proposed research.
